NCT Number: NCT04627727
Official Title: Effect of a Low FODMAP Diet on SIBO Breath Test Positivity
Document Type: Study Protocol and SAP
Document Date: 05/31/2024

PART B STUDY DESCRIPTION

Title of Protocol	Effect of a low FODMAP diet on SIBO
Principal Investigator	[name], MPH

B1. PURPOSE OF PROTOCOL

The primary objectives of this study are to evaluate the following in patients with SIBO:

1. The effect of LFD on bloating
2. The effect of LFD on hydrogen and methane levels in patients with bloating

B2. SIGNIFICANCE AND BACKGROUND FOR THE STUDY

Bloating is the most common symptom associated with disorders of brain-gut interaction (i.e., functional bowel disorders) such as irritable bowel syndrome, a disorder characterized by abdominal pain and altered bowel habits which affects up to 11% of world population. A common cause of bloating is small intestinal bacterial overgrowth (SIBO), a condition defined by excessive and/or abnormal type of bacteria in the small bowel. The potential role of SIBO for irritable bowel syndrome (IBS) was initially proposed by Pimentel et al. Using lactulose breath tests (LBTs), 78% of patients with IBS were also diagnosed with SIBO. After antibiotic therapy, 48% of patients no longer met the Rome criteria for IBS. A recent systematic review and meta-analysis concluded that the prevalence of SIBO is increased in IBS.

Dietary factors are known triggers of IBS related symptoms up to 65% of IBS patients report symptoms attributed to food. In double-blind, randomized, placebo-controlled trials; fructose and fructans have been shown to induce IBS symptoms in a dose-dependent manner.⁵ In fact, a diet low in fermentable, oligosaccharides, disaccharides, monosaccharides, and polyols (FODMAPs) is the most extensively investigated dietary intervention in IBS. A recent meta-analysis of seven randomized controlled trials comparing a low FODMAP diet (LFD) with various control interventions in 397 participants suggested a 31% greater likelihood in improvement of global IBS symptoms. In patients with diarrhea predominant IBS (IBS-D), Eswaran et al showed that those randomized to LFD had greater reductions in daily scores of abdominal pain, bloating, stool frequency, stool consistency, and urgency than the modified National Institute for Health and Care Excellence (NICE) diet. Others have also shown objective improvement in stool consistency of IBS-D patients with LFD using King's stool chart.

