Despite the clinical efficacy of LFD in improving symptoms of IBS-D, its mechanism of action is not clear. Recently, Zhou et al have shown FODMAPs induce colonic tight junction dysfunction and visceral hypersensitivity in rat models, both of which are reversible when rats were fed an LFD. They further showed that this effect of FODMAPs is mediated by microbial dysbiosis and elevated fecal lipopolysaccharide level. However, studies evaluating the effect of LFD on colonic permeability of humans are lacking. Studies have shown significant differences in intra-individual luminal and mucosal microbiome of patients with functional gastrointestinal disorders as well as an increase in *Prevotella* abundance in IBS patients with SIBO as compared with IBS patients without SIBO. Thus, the exact effect of FODMAP on intestinal permeability and mucosal microbiome in humans is not clear and needs further evaluation.

Several studies have also shown increase in the number of mast cells in the colonic mucosa of IBS patients. Although diet is perceived as an important trigger for mucosal mast cell increase and activation reported in IBS-D, it has been poorly investigated. The above reported study by Zhou et al also reported increase in colonic mast cell in rats fed on high FODMAP diet.

B3. DESCRIPTION OF RESEARCH PROTOCOL

A. Study Design – Overview, Methods, Procedures

Study Design

Consenting patients fulfilling the inclusion and exclusion criteria will undergo a 7-day screening period to assess baseline symptoms and then go on a 3-week low FODMAP diet. The total study duration will be approximately 5 weeks with visits at screening and Day 21.

Screening Visit

- Informed consent will be obtained from the subjects.
- Medical history including IBS and SIBO history will be obtained from the subjects
- Blood samples will be obtained
- Glucose SIBO breath test
- Daily questionnaires. Subjects will be instructed on the online daily questionnaires (described below) to be completed for the duration of the study.
- Subjects will be given two stool collection kits for at-home collection. One stool sample will be collected prior to beginning the treatment period. One stool sample will be collected on Day 21.

Visit 2 (Start of Diet/Day 0)

- Subjects will start the low FODMAP diet. Subjects will be told to ingest only Epicured provided items (excluding water) and to avoid eating anything outside of Epicured provided items.
- Baseline stool sample will be returned

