The Patient Reported Outcomes Measurement Information System (PROMIS) is a National Institutes of Health (NIH) set of tools used to provide information on patient outcomes in a variety of fields.
- Gastrointestinal PROMIS scales: PROMIS scales of belly pain, constipation and diarrhea will be administered to assess the severity of belly pain and diarrhea in our patients. PROMIS Belly pain questionnaire and PROMIS diarrhea questionnaire have five and six questions, respectively, which assess symptom severity on a 5 point Likert scale. Higher T-scores on these questionnaires refer to more severe gastrointestinal symptoms.
 - PROMIS belly pain asks how often did you have belly pain, severity of belly pain, interference with activities, bothersomeness and discomfort.
 - PROMIS diarrhea asks how many days did you have loose stools, interference with activities, bothersomeness, and how often you experience urgency.
 - PROMIS constipation asks how often did you experience hard stools, straining and incomplete evacuation.

Blood Collection

Any blood that is remaining after the analysis is completed will be stored frozen indefinitely at BIMDC for use in future studies. The sample will remain de-identified, but be labeled with the unique subject code. Information related to the subject's diagnosis, treatment, and study results will be retained and possibly used in future analysis and more information becomes identified regarding functional bowel disorders. PHI related to the stored samples will not be used in the future analysis and will be kept on BIDMC's secure server. Any samples that may be shared with collaborators will contain the subject code, but will not have any identifiable information or PHI.

B. Statistical Considerations

Sample Size Justification:

This study aims to recruit 30 subjects until 20 subjects are enrolled.

Data Analysis:

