All continuous variables will be tested for normality using the Shapiro-Wilk test. Normally distributed continuous data will be presented as mean (\pm SD) and will be compared pre-and post-dietary interventions using paired Student's t-test. Continuous data which are not normally distributed will be presented as median (range) and compared using Wilcoxon signed-rank test. Proportions will be expressed as percentages and compared using chi-square test or fisher exact test as appropriate. Since we anticipate that most of our tests will involve continuous data that is normally distributed, we based our power analysis on pre-post comparisons using paired t-tests. Assuming two-tailed tests, with alpha set at 5%, a sample size of 20 will provide 80% power to detect a medium effect size (i.e., Cohen's $d=.5$) when the pre-post correlation is $r=.7$.

C. Subject Selection

Patients with functional bloating diagnosed per Rome IV questionnaire and without any alarm features (rectal bleeding, weight loss, nocturnal symptoms, family history of inflammatory bowel disease or celiac disease) will be considered for the study if they had:

- i) Aged 18-65 years at the time of screening

Exclusion criteria

- i) individuals already on a LFD or other dietary restriction such as gluten free diet within the past 6 months
- ii) individuals with peanut, soy, or seafood allergies or insulin-dependent diabetes
- iii) known history of celiac disease, inflammatory bowel disease or microscopic colitis
- iv) prior small bowel or colonic surgery or cholecystectomy
- v) pregnant patients
- vi) antibiotics, excluding topical, in the past 3 months

B4. POSSIBLE BENEFITS

Subjects may experience improvement in their bloating symptoms.

B5. POSSIBLE RISKS AND ANALYSIS OF RISK/BENEFIT RATIO

Blood Drawing

The risks and discomforts of blood drawing from a vein include the possibility of pain or bruising at the site of the blood draw; occasional feeling of lightheadedness; and rarely, infection at the site of the blood draw.

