There is a possible risk of loss of confidentiality, however every effort will be made to ensure patient confidentiality which includes but is not limited to only discussing medical information in a private clinical setting and collecting information necessary to accomplish the research purpose. Physical data will be kept in a locked room that only the research team have access to. Electronic data will be kept on the secure server with access granted only to the individuals on the research staff.

B6. RECRUITMENT AND CONSENT PROCEDURES

Recruitment

Patients will be identified in the following ways:

- Clinical practice of the Center for Functional Bowel Disorders and GI Motility at BIDMC
- GI referrals from BIDMC
- Review of medical records, data repositories, and appointment logs
- Clinical Query 2
- Advertisements

Recruitment letters or postcards with opt-in information will be mailed to potential study participants identified through Clinical Query 2, GI referrals, and review of medical records, databases, and appointment logs. A study coordinator will also be present in the motility lab where the breath tests are conducted to recruit any potential study participants.

Participants who are recruited through the means listed above will then be contacted by phone and a brief phone screening will be initiated to assess the subject's eligibility before scheduling the office visit.

Consent

During the screening visit the Investigator will fully explain the purpose of the study to the patient and all questions and concerns regarding the study will be addressed as well (informed consent process) in a private area in the Division of Gastroenterology.

B7. STUDY LOCATION

Privacy

Every effort will be made to ensure the patient's privacy which includes but is not limited to only discussing medical information in a private clinical setting and collecting information necessary to accomplish the research purpose.

Physical Setting

Study visits will be conducted in the Division of Gastroenterology

B8. DATA SECURITY

Physical data will be kept in a locked room that only the research team has access to. Electronic data will be kept on BIDMC server.

B9 Multi-Site Studies

Is the BIDMC the coordinating site? Yes No

Is the BIDMC PI the lead investigator of the multi-site study? Yes No

B10 Dissemination of Research Results

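### The primary objectives concern patients with SIBO, but the plan enrols functional bloating, requires no breath-test result and defines no SIBO-positive analysis set

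*Combined protocol and SAP*

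**What the plan says.** - **B1, Purpose of Protocol.** The stem reads "The primary objectives of this study are to evaluate the following in patients with SIBO". Objective 2 beneath it reads "The effect of LFD on hydrogen and methane levels in patients with bloating", so B1 names two populations.
- **B3.C, Subject Selection.** Eligible subjects are "Patients with functional bloating diagnosed per Rome IV questionnaire and without any alarm features". The only listed inclusion item is age 18 to 65. None of the six exclusions concerns SIBO or a breath test. B3.A adds a need for Internet access.
- **B3.A, Screening Visit and Final Visit.** Each lists a "Glucose SIBO breath test". No positivity cut-off is given and no result is linked to eligibility. SIBO history is taken but not required.
- **B3.B, Statistical Considerations.** "This study aims to recruit 30 subjects until 20 subjects are enrolled". The power statement is that "a sample size of 20 will provide 80% power to detect a medium effect size" (d=0.5, r=0.7, two-sided 5%). It names no population, and the Data Analysis text defines no SIBO-positive set or subgroup.
- **B6, Recruitment.** "A study coordinator will also be present in the motility lab where the breath tests are conducted to recruit any potential study participants". This is one route among several; the others include clinic, referrals, record review and advertisements.

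**The concern.** The population in which the primary question is asked is not the one that the entry criteria select. B2 presents SIBO as one common cause of bloating, so the protocol itself does not treat the two as the same. A trial that followed the plan exactly could attach a SIBO conclusion to subjects of whom an unknown number had SIBO.

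Three things are at stake.

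- **The estimand.** The pre-post change in all enrolled subjects is an effect in functional bloating. The official title concerns breath-test positivity, and a subject who is negative at baseline cannot convert from positive to negative. That result therefore depends directly on who was positive at the start.
- **Power.** The stated figure carries over to SIBO only if every subject is positive.
- **Freedom to choose.** With no population or cut-off fixed, the subjects who carry the SIBO conclusion can be selected after the data are seen.

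**Working it through.** **1. The plan's own power figure.** Inputs from B3.B: n=20, d=0.5, r=0.7, two-sided alpha 5%, paired t-test.

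The SD of the change, in units of the raw SD, is sqrt(2(1−r)) = sqrt(0.6) = 0.775. So dz = 0.5/0.775 = 0.6455. Noncentral t with 19 df gives power 78.2%; n=21 gives 80.3%. The plan's 80% is reproduced to within 2 points, and 78.2% is the comparator below.

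**2. Assumed share positive.** The documents give no glucose-test positivity rate in functional bloating. The only figure is in B2, "78% of patients with IBS were also diagnosed with SIBO", which comes from lactulose testing in IBS: a different test and a different population. I use 30%, 50%, 60% and 78% as assumptions.

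**3. SIBO question answered in the positive subset.** The subset has m = 20p subjects and the effect is the plan's own. The 95% CI half-width for the mean change is t(0.975, m−1) × sqrt(0.6/m), in raw SD units.

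| Share positive | m | Power | CI half-width |
|---|---|---|---|
| 30% | 6 | 25.2% | 0.81 SD |
| 50% | 10 | 44.6% | 0.55 SD |
| 60% | 12 | 53.2% | 0.49 SD |
| 78% | about 16 | 67.5% | 0.41 SD |
| 100% | 20 | 78.2% | 0.36 SD |

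**4. All 20 pooled.** Positives change by 0.5 SD and negatives by δ. The average effect is d = 0.5p + δ(1−p), with the SD of change held at sqrt(0.6). Example: p=0.5 and δ=0 give d=0.25, dz=0.323, power 27.8%.

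| Share positive | δ = 0 | δ = 0.25 SD | δ = 0.5 SD |
|---|---|---|---|
| 30% | 13.0% | 42.9% | 78.2% |
| 50% | 27.8% | 53.8% | 78.2% |
| 60% | 37.6% | 59.2% | 78.2% |
| 78% | 57.0% | 68.4% | 78.2% |

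Adding the between-group variance p(1−p)(0.5−δ)² to 0.6 lowers these by at most 3 points. If negatives respond as positives do, no power is lost.

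**5. If a positive test were required for entry.** Twenty positives from 30 recruits needs 20/30 = 67% positivity on average. Treating the 30 as unselected, otherwise eligible subjects who are all tested, the binomial probability of at least 20 positives is 4.9%, 29.1% or 95.2% at 50%, 60% or 78% positivity.

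**The case against.** The best counter-reading is that SIBO is the outcome and bloating the population. Objective 2 and the official title both fit that, and section C matches it; the defect would then be one loose phrase in the B1 stem. This reading is reasonable and is the one that the cheapest fix adopts. But the stem governs both objectives and says otherwise, so the text still has to be changed.

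A second argument is that a SIBO criterion was intended. The inclusion list has a single item that does not fit its lead-in, and recruiting 30 to enrol 20 leaves room for a breath-test gate. Nothing in the text states either. If an item was lost, restoring it would be the correction.

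Third, the screening tests allow a positive subset to be identified later. That is true, so the data could address the SIBO question. The plan, however, neither defines that subset nor gives a cut-off, and a subset defined afterwards is post hoc.

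Fourth, the size of the harm is not fixed by the documents. This stands: the positivity rates and the response of negatives are assumed, and the range includes no loss. The screening odds in step 5 also assume unselected recruits, whereas B6 describes phone screening and recruitment in the breath-test lab. The figures are illustrative. The mismatch itself does not depend on them.

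**Conclusion.** The concern holds and must be fixed before analysis. In the text available, B1 asks about patients with SIBO, section C enrols functional bloating, and nothing in B3 or B6 bridges the two. The primary analysis as written does not estimate the effect in the population named in B1.

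The plan's power calculation is arithmetically acceptable, but it describes 20 subjects of unspecified SIBO status. On its own effect size, a SIBO-positive subset would have roughly 25% to 68% power across the assumed 30% to 78% positivity. The cost to a pooled analysis ranges from severe to none, depending on a response in breath-negatives that the documents do not state. Confidence in the contradiction is high; the size of its effect rests on assumptions.

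**What to change.** Make B1 and section C name the same population.

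- **Cheapest option.** Restate the B1 stem, and the conclusion to be drawn, as applying to patients with functional bloating. State that the power figure refers to that population. Pre-specify that bloating, hydrogen and methane levels, and breath-test positivity are also reported in subjects positive on the screening glucose test, as estimates with confidence intervals and with cut-offs fixed before analysis. The titles can stand if positivity is treated as an outcome.
- **Cost.** Wording plus one subset report from tests already planned. The claim becomes less specific to SIBO and the subset will be small and imprecise. Selecting on the baseline breath value also brings regression to the mean in a pre-post comparison, which the report should acknowledge.
- **Alternative.** Requiring a positive screening test for entry would also resolve the mismatch. It carries the same regression to the mean and adds screen failures, and 30 recruits may not yield 20 positives.
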